2.4. INTERVENTION

Embolizations may be performed using the 30-60 μ m or 50-100 μ m size HepaSphere Microspheres. Embolic size is determined by the Investigator based on their judgment of tumor size and vascularity.

2.5. SAMPLE SIZE

This prospective registry is observational and single arm, so there are no cohorts on which to perform comparisons or sample size calculations. A minimum sample size of 100 patients was chosen as being similar in size to studies conducted by Aliberti (N=82) and Fiorentini (N=74) for a similar product CE marked for the same indication.

2.6. STUDY PROCEDURE

Study subjects (once screened, enrolled, and consented) must undergo a complete baseline evaluation. The evaluation includes haematology and serum chemistry assessments and imaging (CT or contrast-enhanced MRI of the liver).

Subjects must have two TACE cycles. A TACE cycle is defined as one embolization for patients with unilobar disease or two embolizations for subjects with bilobar disease (one for each lobe of the liver). The second TACE cycle should be performed within 2-4 weeks after the first TACE cycle. Subsequent TACE cycles may be performed for residual or new disease as needed (at the investigators discretion), based on tumor response. See 'Schedule of Procedures' below for additional information.

Schedule of Procedures

	Screening ¹	TACE Procedure ²	Follow Up Visits ³	Survival Follow-up ⁴
Informed Consent	X			
Eligibility criteria assessment	X			
Demographics	X			
Medical History	X			
Tumor Evaluation / Imaging	X		X	
Hematology / Serum Chemistry	X			
Embolization procedures (TACE)		X		
Pharmacokinetic Sampling ⁵		X		
Additional cancer treatments			X	
Adverse Events		X	X	
Survival status				X

¹ Screening imaging must be within 4 weeks of first TACE cycle.

² First TACE cycle must be within 4 weeks of screening imaging. If the patient has bilobar disease, the embolization of the first lobe must be within 4 weeks of screening imaging and the second lobe must undergo embolization within 3 weeks (\pm 2 weeks) of the first lobe. A second TACE cycle is required for all patients 2-4 weeks after the first TACE cycle. Additional TACE cycles can be performed for residual or new disease as needed.

³ Follow up Visits will start 4-6 weeks after the second TACE cycle and occur every 12 weeks (\pm 2 weeks) thereafter during the first year of follow-up. Follow-up may be more frequent if medically indicated.

⁴ If patients are no longer indicated for TACE, they will continue to be followed for survival for 2 years after the first TACE procedure, with contacts performed every 3 months (\pm 2 weeks).

⁵ Blood samples will be drawn for PK analysis from a portion of study patients after the first TACE procedure at the following time points; 30 min, 1 hour, 4 hours, 12 hours, and 24 hours or prior to discharge (whichever comes first).

3. ANALYSIS POPULATION

3.1. EFFICACY ANALYSES

All patients who have at least one TACE procedure and who have at least one post-baseline tumor evaluation will be included in the efficacy analyses.

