7.1 Primary Efficacy Analyses

Median Overall Survival

The primary efficacy analyses of median overall survival will be performed when all subjects enrolled have reached two years of long-term survival follow up or have died, whichever comes first.

Survival time will be calculated (in months) utilizing the date of the first TACE procedure and the date of death (from any cause), or lost to follow up.

Median overall survival times will be calculated using the Kaplan-Meier (product-limit) method and corresponding 95% confidence intervals will be generated. One- and two-year survival rates and corresponding 95% confidence intervals will also be calculated.

In order to assess the consistency of observed treatment effect across investigational sites, a data poolability analysis will be performed on the primary efficacy outcomes of overall survival. Median overall survival data will be summarized by site, including Kaplan-Meier plots.

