1. STUDY OBJECTIVES

1.1. PRIMARY OBJECTIVE

The primary study objective is the median overall survival of subjects treated with HepaSphere Microspheres loaded with irinotecan. Analysis will be performed when all subjects enrolled have been followed for survival for two years (24 months), are considered lost to follow up, or have died, whichever comes first. Survival time will be calculated in months and utilize the date of the first TACE procedure, the date of death (from any cause), and/or the last successful contact with the subject before they were considered lost to follow-up.

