2.3. STUDY POPULATION

Subjects (meeting inclusion/exclusion criteria and having signed informed consent) will be included in the study analysis if they have had at least one protocol specified TACE procedure.

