3.2. SAFETY ANALYSES

All patients who have at least one TACE procedure will be included in the safety analyses (safety summary).

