5. STATISTICAL METHODOLOGY

5.1. GENERAL METHODOLOGY

Analysis will be performed when all subjects enrolled have been followed for survival for two years (24 months) from the date of their first TACE, are considered lost to follow up, or have died, whichever comes first.

For continuous variables, outputs will be presented with mean, standard deviation (SD), median, minimum, and maximum values. Mean and median will be rounded to a single decimal while SD will be rounded to two decimals. When appropriate, a corresponding 95% confidence interval (CI) will be calculated. Categorical variables (e.g., sex and race) will be reported using frequencies and percentages. All percentages will be rounded to single decimal. If percentages do not add up to 100% due to rounding, a footnote mention will be provided accordingly.

Correlation analyses will be used to analyze relationships for continuous variables. Fisher's exact test will be used to analyze relationships between categorical variables. P-values less than or equal to 0.05 will be considered significant. All p-values will be rounded to 3 decimal places and will be presented as "<0.001" if less than 0.0005.

Survival analyses will be performed using Kaplan-Meier with corresponding median survival times and 95% CIs.

Descriptive statistics will be used to examine demographic and baseline characteristics and to perform other efficacy analyses.

Each table generated will have headers that include the total sample size (N). Frequencies and percentages for categorical variables will be calculated using the number of subjects (n) with non-missing values.

DATA SOURCE

All data will be extracted from Medidata. Datasets will be merged and cleaned prior to data analysis. Data processing procedures will be documented to ensure replicability and error checking.

REPORTING OUTPUTS

SAS 9.4® and SPSS 27.0® will be used to produce all statistical analysis and figure outputs. Tables will be formatted through Microsoft® Word.

HANDLING OF MISSING DATA

There will be no imputation of missing data as the study is observational and all analyses performed should not require such methods.

SITE POOLING

To assess the consistency of observed treatment effect across investigational sites, a data poolability analysis will be performed on the primary efficacy outcomes of overall survival. Median overall survival data will be summarized by site, including Kaplan-Meier plots.

CLASSIFICATION OF PROTOCOL VIOLATION

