Outcomes	mRECIST (N =83) n (%)	RECIST 1.1 (N = 78) n (%)	p-value
Best Tumor Response	0.xxx		
CR	xx (xx.x)	xx (xx.x)	
PR	xx (xx.x)	xx (xx.x)	
SD	xx (xx.x)	xx (xx.x)	
PD	xx (xx.x)	xx (xx.x)	

Note: Percentages may not add up exactly due to rounding

Table 7. Additional TACE Cycles

Outcomes	Standard TACE Cycles (N=76)	Additional TACE Cycles (N=29)	Log rank test	Fisher's exact test
Median Overall Survival (in months)	xx.x	xx.x	p = 0.xxx	
Best Tumor Response: n (%)				p = 0.xxx
CR	xx (xx.x)	xx (xx.x)		
PR	xx (xx.x)	xx (xx.x)		
SD	xx (xx.x)	xx (xx.x)		
PD	xx (xx.x)	xx (xx.x)		
Not Assessed	xx (xx.x)	xx (xx.x)		

Note: Percentages may not add up exactly due to rounding

Table 8. PK Analyses

Variables	N	Mean	SD	Median	Min	Max	R (p-value)
Irinotecan (ng/ML): 30 minutes	xx	xxx.x	xxx.xx	xxx	xxx	xxx	
with Overall Survival							x.x (0.xxx)
with Tumor Response							x.x (0.xxx)
with Treatment-Related AEs							x.x (0.xxx)
Irinotecan (ng/ML): 1 hour	xx	xxx.x	xxx.xx	xxx	xxx	xxx	
with Overall Survival							x.x (0.xxx)
with Tumor Response							x.x (0.xxx)
with Treatment-Related AEs							x.x (0.xxx)
Irinotecan (ng/ML): 4 hours	xx	xxx.x	xxx.xx	xxx	xxx	xxx	
with Overall Survival							x.x (0.xxx)
with Tumor Response							x.x (0.xxx)
with Treatment-Related AEs							x.x (0.xxx)
Irinotecan (ng/ML): 24 hours	xx	xxx.x	xxx.xx	xxx	xxx	xxx	
with Overall Survival							x.x (0.xxx)
with Tumor Response							x.x (0.xxx)
with Treatment-Related AEs							x.x (0.xxx)
SN38 (ng/ML): 30 minutes	xx	xxx.x	xxx.xx	xxx	xxx	xxx	
with Overall Survival							x.x (0.xxx)
with Tumor Response							x.x (0.xxx)
with Treatment-Related AEs							x.x (0.xxx)
SN38 (ng/ML): 1 hour	xx	xxx.x	xxx.xx	xxx	xxx	xxx	
with Overall Survival							x.x (0.xxx)
with Tumor Response							x.x (0.xxx)
with Treatment-Related AEs							x.x (0.xxx)
SN38 (ng/ML): 4 hours	xx	xxx.x	xxx.xx	xxx	xxx	xxx	
with Overall Survival							x.x (0.xxx)
with Tumor Response							x.x (0.xxx)
with Treatment-Related AEs							x.x (0.xxx)
SN38 (ng/ML): 24 hours	xx	xxx.x	xxx.xx	xxx	xxx	xxx	
with Overall Survival							x.x (0.xxx)
with Tumor Response							x.x (0.xxx)
with Treatment-Related AEs							x.x (0.xxx)

[figure not shown]
[figure not shown]
[figure not shown]
[figure not shown]
Figure 1. Kaplan-Meier survival curve for overall survival**Figure 2. Kaplan-Meier survival curve for progression free survival**

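### As written, primary overall survival falls in an efficacy set that requires a follow-up scan, while the objective and the Table 7 shell point to all treated patients

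*SAP*

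**What the plan says.** **Text that puts OS in the scan-required set**

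- SAP 3.1, and Protocol 7.0 (Analysis Population) in the same terms: treated patients "who have at least one post-baseline tumor evaluation will be included in the efficacy analyses". Neither makes an exception for survival.
- Protocol 7.1 labels OS as efficacy: "The primary efficacy analyses of median overall survival will be performed when all subjects enrolled have reached two years" of follow-up or have died.
- SAP 5.1 (Site Pooling) uses the same label: "a data poolability analysis will be performed on the primary efficacy outcomes of overall survival".
- SAP 3.2 defines a set of all treated patients but attaches it to the safety summary.

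**Text that points to all treated patients**

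- SAP 1.1, repeated in Protocol 2.1: "The primary study objective is the median overall survival of subjects treated with HepaSphere Microspheres loaded with irinotecan". There is no scan condition.
- SAP 2.3: subjects "will be included in the study analysis if they have had at least one protocol specified TACE procedure".
- SAP 2.1 follows every enrolled and treated subject for survival and gives site counts of 100 and 5.
- The Table 7 shell in SAP 6.2 reports median OS for columns of 76 and 29 patients and has a response row for patients not assessed.

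**Text that could have settled it but does not**

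- SAP 4.2 names the efficacy population for objective response. The OS sections (SAP 4.1 and 5.2) name no population.
- SAP 5.1 says every table header will carry its N. The Table 4 shell, which holds the primary OS result, has none.

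**The concern.** Death can be observed without imaging, and the survival clock starts at the first TACE. A rule that admits a patient to the OS analysis only after a later scan makes early survival a condition of entry (immortal-time selection). Patients who die before any follow-up scan leave the numerator and the denominator together. The median and the 1- and 2-year rates then move upward.

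OS is the only primary outcome of a single-arm study with no test or threshold attached, so the estimate and its interval are the result. Two analysts following different sections of this SAP could report different primary results, and both could cite the plan.

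**Working it through.** **1. Which N does each shell use?** The sites give 100 + 5 = 105 (SAP 2.1). Table 7 gives 76 + 29 = 105. Tables 1 and 3 both show N = 105. The one shell that shows OS with an N therefore covers every treated patient, scanned or not. Tables 5 and 6 use 83 (mRECIST) and 78 (RECIST 1.1). These are response denominators and are not stated to be the efficacy set, so they are not used below.

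**2. When is the first scheduled scan?** The second TACE cycle is 2–4 weeks after the first, and the first follow-up visit is 4–6 weeks after the second (SAP 2.6). That gives 2 + 4 = 6 to 4 + 6 = 10 weeks, or t = 1.38 to 2.30 months. Staged bilobar treatment is later: 3 + 4 + 3 + 6 = 16 weeks under the 3-week limit in Protocol 5.2, or 5 + 4 + 5 + 6 = 20 weeks under the 3 ± 2 weeks in footnote 2 of the schedule. Those two intervals differ and should be reconciled.

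**3. Size, as an illustration.** The documents do not give the number of early deaths. Assumed medians m come from Protocol 1.0: 19 and 24 months (whole cohorts), 21 months (under 25% liver involvement) and 7 months (26–50% involvement, also eligible). Survival is assumed to be S(u) = 2^−(u/m)^k, with every death before t removed:

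- deaths removed = 105 × (1 − S(t))
- new median = m × (1 + (t/m)^k)^(1/k), which is m + t when k = 1
- new rate at time u = S(u)/S(t)
- SE of the median = m/(k × ln 2 × √105)

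Example, k = 1, m = 21, t = 1.38: deaths removed = 105 × (1 − 2^−0.0657) = 4.7; new median = 22.38; SE = 21/(0.693 × 10.25) = 2.96; shift/SE = 0.47.

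Each pair below is for 6 / 10 weeks.

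| k | m (months) | Deaths removed | Rise in median (months) | Rise ÷ SE | 1-year rate, % |
|---|---|---|---|---|---|
| 1 | 7 | 13.4 / 21.4 | 1.38 / 2.30 | 1.40 / 2.33 | 30.5 → 34.9 / 38.3 |
| 1 | 19 | 5.2 / 8.5 | 1.38 / 2.30 | 0.52 / 0.86 | 64.5 → 67.9 / 70.2 |
| 1 | 21 | 4.7 / 7.7 | 1.38 / 2.30 | 0.47 / 0.78 | 67.3 → 70.4 / 72.6 |
| 1 | 24 | 4.1 / 6.7 | 1.38 / 2.30 | 0.41 / 0.68 | 70.7 → 73.6 / 75.6 |
| 1.5 | 7 | 6.2 / 12.8 | 0.40 / 0.85 | 0.61 / 1.30 | 21.1 → 22.4 / 24.0 |
| 1.5 | 19 | 1.4 / 3.0 | 0.25 / 0.53 | 0.14 / 0.30 | 70.6 → 71.6 / 72.7 |
| 1.5 | 21 | 1.2 / 2.6 | 0.24 / 0.50 | 0.12 / 0.26 | 74.1 → 75.0 / 76.0 |
| 1.5 | 24 | 1.0 / 2.1 | 0.22 / 0.47 | 0.10 / 0.21 | 78.3 → 79.0 / 79.9 |

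The exponential 2-year rate rises by about 2–4 points at 19–24 months (for example 45.3% → 47.4 / 48.9% at 21 months) and by 1–2 points at 7 months.

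**4. Other cases.** If half of the pre-scan deaths had an earlier unscheduled scan, the exponential rise falls to about 0.7 / 1.1 months. If missing scans are unrelated to survival, the expected rise is 0 and only precision is lost. A Kaplan-Meier simulation (3,000 runs, N = 105, censoring at 24–60 months, exponential survival) gave mean rises of 1.39 / 2.28 months at m = 7 and 1.36 / 2.29 at m = 21, in line with the formula.

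**The case against.** The strongest reply is that this is a drafting slip and the weight of the text favours all treated patients. The objective, the study-population rule, the survival follow-up and the Table 7 shell agree. The scan-required reading takes two steps: the set definition, then the efficacy label on OS. This stands as evidence of intent. It does not settle the matter. Table 7 is an exploratory shell and sets no rule for the primary analysis. SAP 2.3 is general, while SAP 3.1 is the specific section on analysis populations, and a programmer would follow the latter.

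The second reply concerns size, and much of it stands. A constant hazard from day 0 probably overstates early deaths. Eligibility requires a life expectancy of at least 3 months, about 13 weeks, which is longer than the 6–10 week window, and earlier visits are allowed. The k = 1.5 rows show how far the effect shrinks. The 7-month rows apply a subgroup median from a 29-patient series to all 105 patients, so they describe a cohort made up entirely of the worse eligible stratum. Staged bilobar treatment works the other way, because its first scheduled scan is later than 10 weeks.

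A third point adds to the fix. Liver progression-free survival also starts at first TACE and counts death (Protocol 2.2), so it needs a named set too.

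**Conclusion.** The concern holds. As written, the rule for efficacy analyses captures the primary outcome, and other passages contradict it. The textual conflict is certain; the harm is conditional. If the scan rule is applied to OS and unscanned patients are mainly early deaths, the median and the survival rates are biased upward.

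For a first scan at 6–10 weeks, the plausible rise in the median runs from 0 to 2.3 months. It is about 0.2–0.5 months (0.1–0.3 SE) with a lower early hazard and medians of 19–24 months, and 1.4–2.3 months (0.4–0.9 SE) under exponential survival at the same medians. These figures rest on assumed survival curves and, apart from the half-scanned and zero-effect cases, on removal of every pre-scan death. If all treated patients are analysed there is no bias. This should be fixed, because it concerns the sole primary estimate and the correction is nearly free.

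**What to change.** - In SAP 3.1 and Protocol 7.0, state that OS, the 1- and 2-year survival rates and the site summaries are analysed in all patients with at least one TACE procedure (105 according to the shells).
- Keep the post-baseline evaluation requirement for the response endpoints.
- Put the OS N in the Table 4 shell.
- In the same edit, name the set for liver progression-free survival and for time to progression.
- If an OS analysis in scanned patients is wanted, label it a sensitivity analysis.

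The cost is a sentence or two in each document and one table header. The protocol revision has to be provided to the ethics committee (Protocol 11.0). No new data are needed, because all enrolled and treated subjects are already followed for survival (SAP 2.1). The one downside is that the reported OS may be somewhat less favourable.

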3.2. SAFETY ANALYSES

All patients who have at least one TACE procedure will be included in the safety analyses (safety summary).

4. OUTCOME VARIABLES

4.1. PRIMARY OUTCOME

Patient survival will be calculated in months from the date of the first TACE procedure until a date of death is obtained or the subject is lost to follow up (utilizing the last successful contact with the patient). Median overall survival time will be the primary outcome of the study.

4.3. OTHER PARAMETERS

Pharmacokinetic (PK) Analyses

PK blood samples drawn from a portion of the subjects after the first TACE cycle (at four pre-determined time periods) will undergo bioanalytical analysis using validated assays. The assays will measure the subject's plasma concentrations of irinotecan and its active metabolite, SN38.

Additional TACE Cycles

Overall survival time will be compared between standard TACE cycles and additional TACE cycles (any TACE procedure(s) beyond the protocol specified number of TACE cycles).

RECIST 1.1

Clinical outcomes will be re-analyzed based on RECIST 1.1 criteria. The best tumor response will be compared between mRECIST and RECIST 1.1.

Clinical Success

Similar to ORR, clinical success will be based on the last post-TACE liver response evaluated through mRECIST and RECIST 1.1 criteria. Clinical success is defined as the total number of confirmed subjects who exhibit a CR or PR [clinical success = (# CR + #PR)].

Demography and Baseline

Subject demographic information and other baseline data will be included and summarized. Sex, age, race, and ethnicity will be included as demographic characteristics. Medical history will be described through system organ class (SOC) and baseline risk factors. Subject hepatic health status such as prior hepatic treatment and tumor location will also be provided.

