irinotecan (FOLFIRI) (Fiorentini 2012). At two years of follow-up, 56% of patients in the TACE group and 32% of those in the FOLFIRI group remained alive; survival dropped to 34% and 9% at 30 months, and 15% and 0% at 50 months among TACE and FOLFIRI patients, respectively. Progression-free survival was 7 months among TACE patients and 4 months among FOLFIRI patients ($p = 0.006$), but time to extrahepatic progression was not significantly different between the two groups. Objective response was observed in 68.6% of analyzed TACE patients and 20% of FOLFIRI patients. Severe neutropenia, diarrhea and mucositis were significantly more common among FOLFIRI patients, and liver enzyme and bilirubin elevations were significantly more common among TACE patients.

A U.S.-based cohort of 55 patients with liver-dominant mCRC who had received prior chemotherapy underwent TACE with irinotecan-loaded DC Beads and was followed for survival (Martin 2009). Adverse events were increasingly common with irinotecan dose escalation (50 mg to 200 mg). At 12 months of follow-up, 8 patients (15%) had complete response, 14 (25%) had partial response, 23 (42%) had stable disease and 10 (18%) had progressive disease according to mRECIST criteria (Martin 2011). Median overall survival for the cohort was 19 months, median progression-free survival was 11 months, and median hepatic-specific progression-free survival was 15 months.

Narayanan and colleagues have presented a retrospective analysis of 28 patients with hepatic metastases from CRC treated with irinotecan-loaded DC Bead (Narayanan 2013). These patients underwent one to five TACE procedures, and survived for a mean of 14.1 months. Complete response was observed in 3 (15%) patients, partial response was observed in 6 (30%), stable disease was observed in 4 (20%) and 7 patients (35%) showed progressive disease. The most common adverse events included nausea (47%), abdominal pain (43%), and vomiting (28%).

Only one publication to date has compared the efficacy of irinotecan-loaded HepaSphere Microspheres and DC Beads in the treatment of liver tumors (Namur 2015). In this study, performed in a VX2 rabbit model, treatment with irinotecan-loaded HepaSphere Microspheres resulted in significantly greater tumor necrosis and a significantly smaller area of residual tumor tissue than treatment with irinotecan-loaded DC Beads or bland HepaSphere Microspheres.

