2.3 Additional Analyses

If sufficient data is available, additional exploratory analyses will also be conducted. These may include, but are not limited to:

- Pharmacokinetic (PK) Analyses: Plasma concentrations of irinotecan and SN38 will be analyzed at the following timepoints after the first TACE procedure: 30 minutes, 1 hour, 4 hours, 12 hours, and 24 hours or prior to discharge (whichever comes first).
- Additional TACE Cycles: The relationship between 'Additional TACE cycles,' (defined as cycles a subject may undergo after the protocol specified TACE 1 and TACE 2) and overall survival time (in months)
- RECIST 1.1: Reanalyze clinical outcomes using RECIST 1.1 criteria and compare best tumor response between RECIST 1.1 and mRECIST criteria.
- Clinical Success: Similar to ORR, clinical success will be based on the last post TACE liver response evaluated through mRECIST and RECIST 1.1 criteria. Clinical success is the total amount of confirmed subjects that have a complete or partial response [clinical success = (# CR + #PR)]

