5.2 Transarterial chemoembolization (TACE) procedure(s)

- Each patient must have at least 2 TACE cycles (Lencioni 2014). A TACE cycle is defined as one embolization for patients with unilobar disease or two embolizations for subjects with bilobar disease (one for each lobe of the liver)
 - Note: It is at the investigator's discretion to evaluate the number and size of lesions and determine if embolization of both lobes (bilobar) can occur in a single embolization session or if both lobes should be embolized separately
- The first TACE procedure must be within 4 weeks of the baseline imaging date

- If bilobar disease is treated with two embolizations in a TACE cycle (one per lobe), the second lobe must be embolized within 3 weeks of the first lobe
- The second TACE cycle should be performed within 2-4 weeks after the first TACE cycle
- The maximum Irinotecan dosage per TACE procedure is 100mg (200mg per TACE cycle)
- Liver enzymes should be observed to ensure they return to acceptable levels before performing the next embolization
- Subsequent TACE cycles may be performed for residual or new disease as needed (at the investigators discretion), based on tumor response
- Embolizations may be performed using the 30-60 μ m or 50-100 μ m size HepaSphere Microspheres. Embolic size is determined by the Investigator based on their judgment of tumor size and vascularity
- Pharmacokinetic (PK) Blood samples will be drawn on a portion of subjects following their first TACE procedure at the following time points: 30 minutes, 1 hour, 4 hours, 12 hours, and 24 hours or prior to discharge (whichever comes first)
- Periprocedural Medications and Supportive Treatment
- Investigator will follow institutional standards of care and irinotecan manufacturer's Instructions for Use regarding periprocedural medications and supportive treatment, including:
 - Hydration regimens, sedation protocols, pain management, nausea and emesis prevention, prophylactic antibiotic treatment, and gastric and pancreatic protection

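### The exploratory PK analysis pools and correlates raw irinotecan and SN38 levels without the dose delivered or the lobes treated at the sampled procedure

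*SAP*

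**What the plan says.** **Dose.** Protocol 5.2 states a ceiling, not a fixed dose: "The maximum Irinotecan dosage per TACE procedure is 100mg (200mg per TACE cycle". Appendix B, step 1.0, asks the site to choose the dose to load, up to 100 mg per vial.

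**Lobes.** A cycle is one embolization for unilobar disease and two for bilobar disease. Protocol 5.2 also lets the investigator decide whether both lobes are treated in one session or separately.

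**PK analysis.** SAP 5.4 plans descriptive statistics, including a coefficient of variation, and a Pearson or Spearman correlation of levels with overall survival, tumor response and treatment-related adverse events. The Table 8 shell has one row per analyte and time in ng/mL, with columns for N, mean, SD, median, minimum, maximum and R with its p-value. It has no entry for dose, lobes or a dose-normalised value. SAP 5.1 calls p-values of 0.05 or less significant.

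**Sampling anchor.** Protocol 5.2 says that "samples will be drawn on a portion of subjects following their first TACE procedure at the following time points". Protocol 2.3, the footnote to Protocol Appendix A and the schedule footnote in SAP 2.6 ("Blood samples will be drawn for PK analysis from a portion of study patients after the first TACE procedure") also say procedure. Protocol 7.3 and SAP 4.3 say cycle: "PK blood samples drawn from a portion of the subjects after the first TACE cycle".

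**The concern.** By design, two sampled patients may have received different amounts of irinotecan, in one lobe or in both. A mean and SD of raw levels then describe a mixture of doses. A reader could not separate systemic release from the amount given, or compare the values with other PK data.

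The correlations are open to the same problem. In the case series with this product cited in Protocol 1.0, median survival was 21 months with less than 25% liver involvement and 7 months with 26-50%. Eligibility here (hepatic tumor burden up to 50% of liver volume) covers both groups. If dose or lobes treated follow disease extent, which is plausible but not stated, a raw level can correlate with survival or response with no effect of exposure itself. For adverse events, the protocol's background reports of a cohort treated with another product: "Adverse events were increasingly common with irinotecan dose escalation (50 mg to 200 mg".

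What is at stake is the reading of Table 8. No primary, secondary or safety result depends on it.

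**Working it through.** **The plan's own figure.** The cycle maximum is embolizations per cycle times the per-procedure maximum: 2 × 100 = 200 mg for bilobar disease, which matches Protocol 5.2, and 1 × 100 = 100 mg for unilobar disease. The plan states no PK sample size, dose distribution or power.

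**Model for the share due to dose.** Assume concentration = dose × log-normal error, so levels are proportional to dose.

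- Error variance on the log scale: ln(1 + CV²). This is ln(1.09) = 0.0862 at a dose-normalised CV of 30%, and ln(1.25) = 0.2231 at 50%.
- Share due to dose: Var(ln dose) / [Var(ln dose) + error variance].
- Raw CV: √[(1 + CV²)(1 + c²) − 1], where c² is the squared CV of the dose.

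The upper dose is the stated per-procedure maximum. The lower limits (50 and 75 mg), the even spread of doses between the limits, and the CVs are assumptions.

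| Assumed doses | Var(ln dose) | c² | Share at CV 30% | Share at CV 50% | Raw CV from 30% | Raw CV from 50% |
|---|---|---|---|---|---|---|
| All equal | 0 | 0 | 0% | 0% | 30% | 50% |
| Even over 75-100 mg | 0.0069 | 0.0068 | 7% | 3% | 31% | 51% |
| Even over 50-100 mg | 0.0391 | 0.0370 | 31% | 15% | 36% | 54% |

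Example, 50-100 mg at 30%: 0.0391 / (0.0391 + 0.0862) = 0.31, and √(1.0370 × 1.09 − 1) = 0.36.

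**Effect on a correlation.** In a simulation (1,500 runs per setting) the outcome depended on dose alone. The dose-outcome correlation was 0.3 or 0.5, 20 or 40 patients were sampled, and the CV was 30% or 50%. All these values are assumptions. Each patient had one of two doses with equal chance. This is the widest spread within each range, so dose explains more here than in the table (35-58% for 50 or 100 mg, and 8-19% for 75 or 100 mg).

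| Doses | Mean Spearman rho, raw level | p ≤ 0.05, raw level | p ≤ 0.05, dose-normalised level |
|---|---|---|---|
| 50 or 100 mg | 0.17-0.39 | 11-75% | 4-6% |
| 75 or 100 mg | 0.08-0.23 | 6-28% | 5-6% |

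This shows that the mechanism works and that normalisation removes it when levels are proportional to dose. It does not estimate what happened in this trial.

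**Anchor.** For a unilobar patient, cycle and procedure are the same event. For a bilobar patient treated in two sessions, the second lobe follows within 3 weeks (Protocol 5.2) or 3 weeks ± 2 weeks (schedule footnotes), so the two words point to different events. All the sampling instructions say procedure, with times from 30 minutes to 24 hours.

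**The case against.** The strongest reply is that this is exploratory work, done only if sufficient data are available and to the extent that the PK data allow. If every sampled patient received the same dose, the dose problem disappears. Both points stand, and they limit the severity. They do not answer the gap: without a dose entry in Table 8, a reader cannot tell whether doses were equal.

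A second reply is that the stated question concerns circulating levels. For adverse events, dose may act through the level, so adjusting for dose would remove part of the effect of interest. A dose-normalised level also answers a different question, about release or clearance. This stands, and it is why a blanket adjustment is not recommended.

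A third is multiplicity. Table 8 already holds 2 analytes × 4 times × 3 outcomes = 24 correlations, and further tests add to them. This also stands.

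Two stronger readings are tempting. A reader might infer that treating both lobes in one session doubles the dose behind a sample. If 20% of samples followed a doubled dose, the dose share would be 34-57% and the raw CV about 50-67%. Those figures need sessions above the stated 100 mg per-procedure maximum, and the documents do not say whether that maximum covers both lobes in one session. A reader might also infer from the word cycle that profiles will be matched to the wrong dose. Under the current plan no profile is matched to any dose, and the sampling instructions are consistent.

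**Conclusion.** The point holds as a minor one. The PK summaries may mix doses, and a correlation of level with survival or response may reflect dose or disease extent. The size cannot be found from the documents. The dose share of log-concentration variance starts at zero for equal doses and reaches 15-31% if doses were spread evenly over 50-100 mg. Even then the coefficient of variation rises only from 30% to 36%, or from 50% to 54%. These figures rest on proportional levels, the assumed lower dose limits and the assumed CVs. The 50 mg figure appears in the documents only for the other product's dose-escalation cohort.

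The conflict between cycle and procedure is real but mainly one of wording. The documents do not support the conclusion that samples were taken at the wrong time, or that any correlation in Table 8 will be spurious.

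**What to change.** 1. In SAP 5.4 and Table 8, show the irinotecan dose delivered and whether one or both lobes were treated at the sampled procedure. Report dose-normalised concentrations (ng/mL per mg delivered) beside the raw values.
2. As a sensitivity analysis only, repeat the survival and response correlations with dose-normalised levels or with a rank correlation adjusted for dose.
3. Keep the raw correlation with adverse events, with a note that it includes the effect of dose.
4. In Protocol 7.3 and SAP 4.3, replace first TACE cycle with first TACE procedure, as in the sampling instructions.
5. Reconcile, within Protocol 5.2, whether the per-procedure maximum applies when both lobes are treated in one session. This review takes no position on which reading is right.

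Nothing planned is removed and no new sampling is needed. The cost is a few columns and, with one sensitivity method, 2 × 4 × 2 = 16 further exploratory tests. The number of PK patients is not stated, so cells may be small if results are split by lobes; that split is best kept descriptive. The changes rely on dose and lobes being recorded for each procedure, which is assumed.
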